	
be conducted using the block randomization method, based on the FTO gene allele. This process will involve two sample randomization blocks: one for A carriers allele and another for T homozygous individuals. Each block will then be randomized and divided into two groups, maintaining a 1:1 ratio between control and dietary intervention. Following randomization, four groups will be formed: two groups receiving the Balanced Nutrition Diet intervention (DAC: A allele carriers + Diet; and DTH: homozygous T allele + Diet), and two control groups (CAC: A allele carriers; and CTH: homozygous T allele). Nutrition education will be provided to all groups. The intervention period will span 4 weeks (28 days), after which a second blood draw will be conducted to gather endline data.
 
The Balanced Nutrition Diet is meticulously designed to supply the body with nutrients in suitable types and quantities, adhering to the principles of food diversity which include variety, balanced proportions, correct amounts, and consistency. Additionally, it emphasizes the "Fill My Plate" guideline, advocating for the consumption of all five food groups daily or at each meal. Portion sizes of the Balanced Nutrition Diet are structured according to the "Balanced Nutrition Tumpeng" model, encompassing 3-4 portions/day of carbohydrates, 2-3 servings/day of fruit, 3-4 servings/day of vegetables, and 2-4 servings/day of side dishes, with restrictions set at 4 tablespoons of sugar, 1 teaspoon of salt, and 5 tablespoons of oil per day, alongside a recommendation of drinking 8 glasses of water daily.
 
During the intervention period, food is provided three times a day - breakfast, lunch, and dinner - following a 28-day menu cycle. The researcher bears the sole responsibility for covering the cost of all food provided to the intervention group during this 28-day period. The Balanced Nutrition Diet offered adheres to specific macronutrient distribution ratios of 45-55% carbohydrates, 15-20% protein, and 20-25% fat, as outlined by Almatsier (2010). Complex carbohydrates, such as whole grains, are prioritized, while protein sources lean towards low-fat options, with half derived from plant-based sources. Monounsaturated and polyunsaturated fats are favored, and organic ingredients are preferred whenever possible.
 
Each meal's composition adheres to the "Fill My Plate" principle, and daily portions follow the "Balanced Nutrition Tumpeng" concept. Specifically, the diet provided by Eat & Fit Catering adheres to certain guidelines, including cooking methods that eschew fire and oil frying in favor of boiling, sautéing, or roasting techniques. Canola oil is the preferred oil, sodium-reduced salt is utilized, and mushroom stock serves as the primary flavouring agent, ensuring both healthfulness and taste. For each subject, energy requirements were calculated according to resting energy expenditure (REE) estimates using Mifflin-St. Jeor Equation (Mifflin et al. 1990). REE is then multiplied by the physical activity level (PAL) according to WHO-FAO that has been obtained.
 
REE (women)= (9.99 x Body Weight) + (6.25 x Height) + (5 x Age) – 161
 
The dietary distribution to subjects occurs three times, facilitated by couriers from the catering party. Should the delivery fall beyond the catering courier's radius, online delivery services will be utilized, with costs borne by the researcher.
 
In contrast, the control group subjects do not adhere to a specific diet regimen. However, they will receive general guidance on healthy eating habits and will be monitored closely. Nonetheless, their energy requirements will still be assessed based on REE and physical activity levels, as previously mentioned.
 
b) Determination of outcome indicators:
 
Evidence shows that compared with TT wild type, the risk allele A FTO rs9939609 showed significantly higher body weight, body mass index, waist circumference, hip circumference, and waist-to-hip ratio (Mangge et al. 2011; Tupikowska-Marzec et al. al. 2019; Mehrdad et al. According to Chrostowska et al. (2013), evidence is growing that the waist-hip circumference ratio is a stronger indicator of cardiovascular disease than body mass index. The meta-analysis of Gholamalizadeh et al. (2020), showed that carriers of the A allele of the FTO rs9939609 polymorphism had a higher fat percentage. The research results of Dorling et al. (2021) showed

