--	---

	
the FTO SNP rs9939609 was associated with changes in REE adjusted for fat mass and lean mass, with the AA allele showing a decrease compared to TT.
 
Several studies have been conducted looking at the relationship between the FTO rs9939609 genotype and interleukin-6 (IL-6) levels, but only a few have shown real differences (de Luis et al. 2012b; Zimmermann et al. 2011; de Luis et al. 2016; Magno et al. 2018; Hosseini et al. 2011). Studies have also been conducted that there is an association of FTO rs9939609 with higher levels of C reactive protein (CRP) (Fisher et al. 2009; Sun et al. 2010; Lappalainen et al. 2011; Tupikowska-Marzec et al. 2019). However, other studies show contradictions (Zimmermann et al. 2011).
 
Research by Mehrdad et al. (2020a) showed that subjects with A allele carriers (AA and AT) had lower adiponectin levels than wild-type subjects (homozygous TT) with homozygous AA allele types having the lowest values although not significantly different. Several other studies also show the same thing in both obese and other types of adult subjects (Saucedo et al. 2017; Isgin-Atici et al. 2021). However, research by de Luis et al. (2016) and Duicu et al. (2016) showed a contrast, namely that adiponectin levels were lower in the TT genotype group compared to the AA genotype group. Based on what has been explained above, several outcome indicators that will be analyzed are waist-hip circumference, mass and total fat percentage &visceral, interleukin-6 levels, hs-CRP levels, and adiponectin levels.
 
Statistical analysis
 
The data obtained were tested statistically using SPSS statistical software for Windows (IBM version 26.0, SPSS Inc., Chicago, Ill., USA). The normality of variable distribution was verified with the Shapiro-Wilk test. Analysis of Variance (ANOVA) was used for all baseline data. Paired samples t-test was used to see changes in calorie intake, macronutrients, BW, BMI, waist circumference, hip circumference, waist-hip ratio, RM, percent total fat, visceral fat, subcutaneous fat, skeletal muscle, IL-6, hs-CRP, and adiponectin between before and after intervention. Data are presented as mean \pm SD and P < 0.05 was considered statistically significant.
 
c) Planned interim analysis: There is no interim analysis in this study.
 
d) Clinical trial termination procedures: Referring to the guidelines for good clinical trials in Indonesia (POM RI 2016), clinical trials are terminated if clinical trial safety problems occur, such as serious undesirable events and serious side effects of the test product. The principal investigator will report the KTDS to the ethics committee no later than 3 days after the incident is discovered. The possibility of KTDS that could occur in this study is that the patient requires hospital treatment as a result of the intervention process.
 
e) Estimated research time required for one subject per procedure: \pm4 weeks
 
f) Ethical issues (state your opinion about the ethical issues this research may encounter):
 
 • Respect for person (respect for human dignity): Subjects in this study took part based on their own conscious choice, there was no element of coercion. Subjects have the right to be protected, including that all Subject data will be kept confidential. • Beneficence(beneficial) Non-maleficence (not harmful): This research optimizes benefits and minimizes harm to subjects. The results of the research will be useful for society. The research design has been made as clear as possible. Researchers have competencies that are appropriate to the research topic to be conducted. • Justice(justice): Subjects are treated the same/or there is no differentiation between subjects.

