--	--

	There is no conflict of interest
10.	
Adverse Event reporting plan(AE)
 
a. Recording (What will be reported): Each incident must be recorded in detail regarding the time it occurred and the causes to avoid similar incidents and as additional data for research progress reports.
 
b. Analysis and action procedure:
 
 1. Anthropometric Measurements After an overnight fast for 12 hours, all subjects underwent anthropometric evaluation. All individuals were instructed to remove their shoes and wear as light clothing as possible before undergoing measurements. Body weight, mass & percent body fat were measured with a Bioelectrical Impedance Analyzer (BIA). Body height was evaluated using a stadiometer to the nearest 0.1 cm. BMI is calculated using the formula = body weight/height² (kg/m²). Waist circumference and hip circumference were assessed using a flexible steel metric tape to the nearest 0.5 cm. The waist-to-hip ratio (WHR) was analyzed and evaluated according to clinical risk thresholds, equivalent to WHR > 0.9 for men and WHR > 0.85 for women. 2. Blood Sample Analysis A venous blood sample of around 6-10 cc is taken using a sterile syringe by competent licensed medical personnel. The blood is then divided into two different sterile tubes (Vacutainer®). The first tube is a purple cap tube containing EDTA, while the second tube is a yellow cap tube containing separator gel. After that, the sample is put on ice to be immediately taken to the testing site. The samples in the purple tube will then be processed for DNA and RNA isolation. DNA isolates were used for analysis of FTO gene variants using PCR and sequencing. Blood samples in yellow tubes were used for analysis of serum levels of interleukin-6, hs-CRP, and adiponectin using the ELISA method. All blood analyzes will be carried out at the Molecular Genetics Laboratory, FK UNPAD. The remaining samples were stored at -80 °C to be retested if necessary. 
c. Emergency request system: Each subject will be given a contact for researchers and doctors who can be contacted if there are complaints of illness related to the intervention. Researchers and doctors can be contacted 24 hours during the research period regarding interventions for emergency response preparedness. If there is an emergency, the subject will be taken to the emergency room at Hasan Sadikin Hospital.
 
d. Termination of subjects in research due to adverse events: If an undesirable event occurs, it must be immediately reported to the researcher. Researchers will then coordinate with parties who feel it is necessary to carry out follow-up as soon as possible. Then the researcher will assess whether the subject needs to be discontinued in the study after consulting with a clinical trial expert.

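### The contact route for adverse events is worded more narrowly than the recording and reporting rules, and no common way of eliciting events in all four groups is described, so counts by arm could be unequal.

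*Combined protocol and SAP*

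**What the plan says.** Three items of Section B.10 (Adverse Event reporting plan) bear on this.

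- **B.10(a), recording:** "Each incident must be recorded in detail regarding the time it occurred and the causes". There is no limit by arm or cause.
- **B.10(c), contact by the woman:** every woman, in whichever group, is told of study staff "who can be contacted if there are complaints of illness related to the intervention". The next sentence words the 24-hour line in a similar way: "Researchers and doctors can be contacted 24 hours during the research period regarding interventions for emergency response preparedness".
- **B.10(d), termination of subjects:** "If an undesirable event occurs, it must be immediately reported to the researcher". Again there is no limit by arm or by relation to the diet.

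Elsewhere:

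- B.9(d) gives as the possible serious event that "the patient requires hospital treatment as a result of the intervention process".
- B.9(a) says that "the control group subjects do not adhere to a specific diet regimen" and that "they will receive general guidance on healthy eating habits and will be monitored closely". It does not say what the monitoring consists of or how often it takes place. The diet arm receives three catered meals a day for 28 days. All groups receive nutrition education and a second blood draw after the 28 days.
- B.2 marks the trial as open label.
- The outcome indicators in B.9(b) include no safety outcome, and the statistical analysis paragraph has no comparison of adverse events.
- B.10(b) is headed as the analysis and action procedure of the adverse-event plan, but covers only anthropometry and blood handling.
- The case report form items available cover screening only.

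**The concern.** Recording and reporting duties take effect once someone knows that an event has happened. The only reporting route that the available text gives to the women is the contact in B.10(c), and its wording asks a woman to decide first whether her illness has to do with the intervention. That question means different things in the two arms. A diet woman with an upset stomach can readily link it to the catered food. A control woman with the same complaint has no provided food to link it to. Because the trial is open label, each woman answers knowing her arm.

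What is at stake is the background rate that a randomised control group supplies. The summary in B.1 names bacterial contamination of the intervention food as a foreseen hazard. To tell such a problem from ordinary illness, one needs to know how often ordinary illness occurred in controls, ascertained in the same way. Event information is also used without any formal test: B.9(d) provides for stopping the trial on serious events, and B.10(a) sends incidents to progress reports.

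**Working it through.** **1. The items side by side**

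| Item | What it governs | Limited to the intervention? | Says how an event becomes known? |
|---|---|---|---|
| B.10(a) | recording | no | no |
| B.10(c) | contact by the woman | yes, in its wording | yes, by her own call |
| B.10(d) | reporting to the researcher | no | no |
| B.9(a), controls | close monitoring | not stated | no content or frequency given |

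The one item that describes a route for the women is also the one worded narrowly. The wider items do not say how an event comes to light.

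**2. Denominators**

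The sample-size text gives 7 per group and adds 50% for dropout: 7 × 1.5 = 10.5, rounded up to 11. Four groups give 4 × 11 = 44, which agrees with the stated minimum of 44. With 1:1 allocation within each genotype block, that is 22 diet and 22 control.

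**3. Illustration of unequal reporting**

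The documents give no illness rate and no reporting fraction, so every input below except the 22 is an assumption. Let the true 28-day risk of any minor illness, p, be the same in both arms. Let r_D and r_C be the fractions reported in the diet and control arms.

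- Expected women reported per arm = 22 × p × r
- Apparent risk difference = p × (r_D − r_C)

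With r_D = 0.8:

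| p | Diet count | Control count, r_C = 0.8 / 0.4 / 0 | Apparent excess in diet, r_C = 0.8 / 0.4 / 0 |
|---|---|---|---|
| 10% | 1.8 | 1.8 / 0.9 / 0 | 0 / 4 / 8 points |
| 20% | 3.5 | 3.5 / 1.8 / 0 | 0 / 8 / 16 points |
| 30% | 5.3 | 5.3 / 2.6 / 0 | 0 / 12 / 24 points |

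For example, at p = 20% and r_C = 0.4: 22 × 0.20 × 0.8 = 3.5 against 22 × 0.20 × 0.4 = 1.8, and 0.20 × (0.8 − 0.4) = 0.08. The true difference is zero in every row. Equal elicitation (r_C = r_D) removes the expected excess whatever p is.

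**4. Would such a gap look like a signal?**

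Taking Fisher's exact two-sided test as a yardstick (the plan does not specify it), 4 of 22 against 0 of 22 gives P = 0.108 and 5 against 0 gives P = 0.048. So even with no control reports, it takes 5 diet reports to cross 0.05. If all diet-arm illness were reported and none in controls, the binomial chance of 5 or more among 22 is about 6% at p = 10%, 46% at 20% and 84% at 30%. If 40% of control illness were reported instead, the chance of a diet excess with P < 0.05 falls to about 3%, 12% and 21%. The no-report case is therefore an upper bound.

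**The case against.** The strongest reply is that B.10(c) describes an emergency access line, not the rule for counting events. B.10(a) and B.10(d) are the counting and reporting rules, and neither is limited by arm or cause. The contact goes to every woman. Controls are to be closely monitored and are seen for the second blood draw, so the researcher has other chances to hear of illness. All groups have blood draws and education, and B.1 names infection and haematoma from venepuncture as risks, so a control could have a complaint that fits the wording. B.10(a) also requires time and causes to be recorded, which would help trace a common food source.

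Most of this stands, and it rules out three stronger readings that a reader might infer.

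- **That women are told to make contact only for related complaints.** The text does not say *only*.
- **That illness in controls goes uncounted.** Under-reporting is possible, but it is not established. Nor can one say that nobody asks both arms the same question: some pages are not available and the form is cut off, so the most that can be said is that no such question is described in the available text.
- **That the diet's safety result is biased by design.** No safety outcome and no comparison by arm are planned, so there is no planned result to bias.

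What the reply does not settle is how an event in a control comes to light on the same terms as one in the diet arm. Monitoring of unstated content and frequency does not answer that, and the wider duties begin only when an event is known.

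**Conclusion.** The point holds in limited form. B.10(c) is narrower than B.10(a) and B.10(d), and no common, scheduled elicitation in all four groups is described. In an open-label trial where only one arm receives food, following the text as written would tend to under-report background illness in controls relative to the diet arm. The likely direction is against the diet.

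The size cannot be derived from the documents. The range of 4 to 24 percentage points rests on an assumed equal true risk of 10–30%, 80% reporting in the diet arm, and 40% or no reporting in controls, the last being a worst case. The consequence is confined to descriptive safety statements and progress reports. The efficacy outcomes and the planned tests are not touched. This is a cheap improvement, not a flaw that undermines the trial.

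**What to change.** 1. Reconcile B.10(a), B.10(c) and B.10(d), so that the contact, including the 24-hour line, is open for any complaint whatever its cause.
2. State that all women in all four groups are asked the same open question about any illness or symptom at the same contacts, at least at the day-28 visit. If the monitoring of controls is also to be used, give its schedule and apply the same schedule to the diet arm.
3. Record date and severity for each event, and judge relation to the diet only afterwards.
4. Report descriptively the number of women with at least one event by randomised arm. No test is needed.

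**Cost:** a few minutes per woman, one short form, and a higher recorded event count. No change to the diet, the visits or the sample size is needed if the question is put at the day-28 visit.

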[name]. Ir. [name], M.S.

Pembimbing III

[name]. Ir. [name], M.S.

CASE REPORT FORM

Case Report Form is available at: <https://forms.gle/zsCVMFcFvAzZJ6HcA>

7/26/23, 2:43 PM	Case Report Form	7/26/23, 2:43 PM	Case Report Form
Case Report Form Pengaruh Diet Gizi Seimbang terhadap Faktor Risiko Kardiovaskular pada Dua Tipe Gen FTO rs9939609 Wanita Dewasa Muda Obes		5. Pemeriksaan Kesehatan *	
<small>* Indicate required question</small>			
1. Email *		Mark only one oval per row.	
<hr/>		 Normal	 Abnormal
2. Nomor Subjek		 Tekanan	 Darah
<hr/>		 Denyut	 Nadi
Penapisan (Screening)		 Suhu	 Darah
3. Tanggal persetujuan informed consent *		 Gula	 Puasa
<hr/> <small>Example: January 7, 2019</small>			
4. Tanggal Penapisan		<hr/> <small>Example: January 7, 2019</small>	
<hr/> <small>https://docs.google.com/forms/d/1JQ_leactmKYFNPbzkaDO-QwAE1a8cfexE33cOMZvQedit#responses</small>			
1/5		https://docs.google.com/forms/d/1JQ_leactmKYFNPbzkaDO-QwAE1a8cfexE33cOMZvQedit#responses	
2/5			

8. Eksklusi *

Check all that apply.

	Ya	Tidak
Sedang hamil dan menyusul?		
Memiliki riwayat penyakit kronis?		
Rutin konsumsi suplemen atau obat-obatan fitofarmaka?		
Sedang berpartisipasi pada penelitian lain?		

This content is neither created nor endorsed by Google.

Google Forms

6. Antropometri *

Mark only one oval per row.

	Nilai
BB aktual	
TB aktual	
IMT	
Total persen lemak tubuh	
Persen lemak visceral	
Total massa lemak tubuh	
Massa lemak visceral	
Lingkar pinggang	
Lingkar pinggul	
Rasio lingkar pinggang-pinggul	

Kriteria

7. Inklusi *

Check all that apply.

	Ya	Tidak
Obese (IMT>30 kg/m ² dan persen lemak >35%)?		
Etnis Sunda?		
Usia 18-25 thn?		
